#### Hypothesis:

*Hypothesis*: Pre-treatment with IL-2 in patients with highly suspicious pigmented lesions will reduce the incidence of metastatic melanoma compared to the PBS placebo group by initiating an adaptive immune response to native melanoma protein and peptide. *Major Aims*:

- 1) To conduct a pilot study to assess the number of patients needed to analyze in order to achieve a statistically significant differentiation between treatment and control outcomes in study measures including tumor infiltrating lymphocytes (TILs) and circulating immunomodulators.
- 2) To assess the efficacy of intralesional pre-treatment of IL-2 on highly suspicious lesions in generating an adaptive immune response and preventing melanoma metastasis.
- 3) Sub-study To assess if there a difference in specific immune modulators in patients receiving IL-2 pre-treatment compared to patients receiving a placebo.

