This study is a randomized, controlled, double-blind study. Patients with highly suspicious pigmented lesions will be randomly assigned by an algorithm to one of two groups: 1) treatment group patients will be treated intralesionally with IL-2 (Proleukin (Aldesleukin), Novartis Pharmaceuticals Canada Inc.) at a dose of 500,000 International Units (IU) (0.1ml) for 2 treatment cycles 1 week apart (Day 1 and Day 8) Figure 1; 2) control group patients will be treated intralesionally with sterilized sodium chloride (0.9%, m/v) (0.1ml) Figure 1. Randomization will be done at the pharmacy for each patient (generated by a Random Block algorithm). IL-2 (Proleukin) will be obtained from the Provincial Drug Distribution Program by the pharmacy, paid for by [name] research services account (please see budget attached). The pharmacy will prepare either IL-2 treatment (supplied as 1 x 0.8ml (4 million units) or injectable placebo (0.9% sodium chloride) supplied as 0.8ml). The syringes will be prepared by following aseptic technique in a biohazard hood. A 22-million unit vial of IL-2 will be reconstituted with 1.2ml of sterile water for injection and mixed gently. After drawing up 3.2ml of 5% dextrose in water and transferring to the IL-2 vial, the resulting concentration will be 5 million units/ml. 0.8ml of the IL-2 solution will then be drawn into a 3ml syringe. Expiry time of the reconstituted solutions is 48 hours at 4C. The pharmacy will assign a codified ID which will be provided along with the syringe with the patient name labeled as "Interleukin-2/Placebo" (thus blinding study to clinician and patient). As a pilot study, the principle of the design is to test the feasibility of proceeding to a larger and more expensive trial following the methodology and protocol proposed. As such there will be a minimum of 20 (10 treatment, 10 placebo) participants (up to a maximum of 60). It is estimated that statistical significance will be reached with 20 patients, however it is not reached after 20 patients, an additional 10 (5 treatment, 5 control) patients will be enrolled. If significance is still not reached after 30 patients, an additional 10 patients will be enrolled and so on up to a maximum of 60 patients. If after 60 patients, significance is not achieved then further recruitment under the current protocol would not be logical and therefore the methodology would need to be revised or study discontinued.

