All blood, urine, and lesion biopsy samples will be labeled with a codified number (will not contain any patient identifying information) and will be immediately transported to [name] laboratory (Sir Charles Tupper Medical Building, 11F11) at Dalhousie University for storage. Fine needle aspiration of excised samples will be assessed for tumor genetic and epigeneitic profile (Figure 2). Blood and urine will be assessed for proteomic and metabolomic profiles, respectively (Figure 2).

A database containing patient IDs and codified numbers will be restricted to the office of [name] (11th floor, VG). This is a locked office, and the data will only be accessible to the investigators named on this application. This database for will contain patient IDs, and info on disease status, treatment/control, follow up visits, and sample analysis – only info pertinent to the outcome measures. All sample data will be assessed using codified descriptors and will contain no patient ID info. Once the RNA, proteomic, metabolomic and pathology data has been analyzed, unmasking treatment and control groups will be conducted at the VG office of [name], by the named investigators. If the data reaches statistically significance, the study will not accept any more patients, if not, a further 10 patients will be incorporated – to a maximum of 60 patients. Any publications of study results will be completed devoid of any information that could be used to identify patients included in the study.

All study participants will receive biannual assessments for 5 years after the initial intervention to assess disease progression, or the development of new melanoma, to compare between both treatment and control groups. There is no standardize test or measurable biomarker to assess established or lasting immunity. This aspect of the study is identical to the patient assessment conducted as per standard of care for melanoma patients. Again, any publications of study results will be completed devoid of any information that could be used to identify patients included in the study.

	Interleukin 2 Treatment Group				
Interleukin-2 Treatment Group		Placebo Treatment Group			

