#### Analysis of Data

#### Outcome measure/study objectives:

Assessment of Number of Patients Needed to Obtain Significance [**Time Frame: 1 year**] – Data will be analyzed in order to achieve a statistically significant differentiation between treatment and control outcomes in study measures including tumor infiltrating lymphocytes (TILs) and circulating immunomodulators.

Assessment of Metastasis [**Time Frame: 5 years**] - All patients will receive assessments every 4 months for 2 years and then biannual assessments for years 3-5 after the initial intervention to assess disease metastasis in treatment and control groups. Both number of new metastases (integer value) and thickness (mm) will be measured as a part of this assessment.

Sub-Study Outcome Measure:

Assessment of RNA genetic profile **[Time Frame: 5 years]** - RNA analysis of excised tissue will be compared to unaffected patient tissue obtained from the clear margins of the excisional biopsy to assess genetic changes resulting from the melanoma and treatment/placebo injections. RNA analysis will occur at [name] laboratory (Sir Charles Tupper Medical Building, 11F11) at Dalhousie University.

Assessment of Systemic Immune Response: Proteomic Analysis [**Time Frame: 5 years**] - Proteomic analysis will be conducted on blood samples to assess systemic immune response to both treatment and control groups. Serum collected from patient blood samples will be used for proteomic analysis to assess protein expression, including circulating immunomodulators (cytokines and chemokines) before, and after, treatment. Proteomic analysis will occur at Dalhousie's Proteomics and Mass Spectrometric Core Facility located in the Life Sciences Research Institute. This study may serve to help develop diagnostic protocols and methods of assessing response to treatments.

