#### How will the data be analyzed:

All study practices and statistical methods are based on the International Conference on Harmonization (IHC) document "Statistical Principles for Clinical Trials." Data will be summarized by treatment group. Baseline characteristic, safety outputs and a total overall column will be included to summarize all subjects. For all baseline, demographic, safety and efficacy outputs data will be summarized by treatment group. In summary tables of continuous variables, the minimum and maximum statistics, the arithmetic mean and median, the 95% confidence interval, standard deviation, and standard error will be presented will to the same number of decimal places as the original data. In summary tables of categorical variables, counts and percentages will be used. The denominator for each percentage will be the number of subjects within the population treatment group unless otherwise specified. All hypothesis testing will be carried out at the 5% (2-sided) significance level unless otherwise specified. P-values will be rounded to three decimal places. P-values less than 0.001 will be reported as <0.001 in tables.

The treatment label for all tables, listings and figures will be:

Treatment	Label
2 treatment cycles of	IL-2
500,000 IU of IL-2 in 0.1	Treatment
mL	
0.1 mL of sterile saline	Placebo
(0.9% m/v)	
All Treatments	Total

Where that any of the statistical methods described herein prove unsuitable during analysis, more appropriate methods will be used. All changes in methodology will be documented in the clinical study report. Additional ad-hoc analyses may be conducted as deemed suitable.

Subject inclusion/exclusion criteria will be determined at baseline visit, and subjects who do not meet all criteria will not be entered into the study. Those subjects deemed eligible to participate will be allocated a 3-digit number at randomization prior to the initial treatment. If a subject is discontinued at any time after entering the study, the Investigator will ensure this does not affect the patient's standard of care. At the patients request all unused biological samples (blood, urine, and core biopsies) will be immediately destroyed. The reasons for withdrawal will be recorded on the CRF and will be included in the final report. Failure to complete both (2) treatment cycles will result in patient removal from the trial.

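### Stopping at the first p<0.05 over up to five unmasked looks (20 to 60 patients), each at an unadjusted 5%, gives about 13% overall error for one endpoint with a t-type test

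*Combined protocol and SAP*

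**What the plan says.** The Research Plan (randomization and sample size paragraph) sets the range: "there will be a minimum of 20 (10 treatment, 10 placebo) participants (up to a maximum of 60"). It expects 20 patients to be enough but gives no effect size, SD or power. If they are not enough, 5 per arm are added, and then: "If significance is still not reached after 30 patients, an additional 10 patients will be enrolled and so on", up to 60.

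Later in the same section, the paragraph on the database makes this an operating rule. "Once the RNA, proteomic, metabolomic and pathology data has been analyzed, unmasking treatment and control groups will be conducted" by the named investigators, and then: "If the data reaches statistically significance, the study will not accept any more patients, if not, a further 10 patients will be incorporated".

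The section on how the data will be analyzed states: "All hypothesis testing will be carried out at the 5% (2-sided) significance level unless otherwise specified". Nothing else is specified for the repeated looks: no boundary, alpha-spending function or adjusted level. The general reference there to the ICH statistical principles document supplies none.

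The outcome section speaks of "outcomes in study measures including tumor infiltrating lymphocytes (TILs) and circulating immunomodulators" without saying which measure decides. Aim 1 is to "assess the number of patients needed to analyze in order to achieve a statistically significant differentiation". Aim 2 begins "To assess the efficacy of intralesional pre-treatment of IL-2 on highly suspicious lesions" and covers both immune response and metastasis.

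**The concern.** Each look gives chance another opportunity to produce p<0.05, and recruitment ends at the first success. A 5% level per test is then not a 5% level for the trial, yet a significant stop would be reported and read as if it were.

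Two further problems follow.

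- **Undefined decision.** Four kinds of data are analyzed before unmasking, and no endpoint or test is named for the stopping decision. The overall error rate therefore has no definite value.
- **Aim 1.** The number of patients at which p first crosses 0.05 is a random stopping time. Trials stopped for significance also show exaggerated effects on average. If the stopping number, or the effect seen at the stop, were used to size the larger trial, it would mislead.

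**Working it through.** **Inputs from the documents.** Looks at N = 20, 30, 40, 50 and 60; 1:1 allocation (n = 10, 15, 20, 25, 30 per arm); two-sided 0.05 at each look; stop at the first p<0.05.

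**Assumptions.** The documents give no test, effect size, SD, event rate or correlation. All of these below are assumed.

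**1. The stated 5%.** One t-test at 20 patients rejects in 5.0% of null trials. The stated level is right for a single look.

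**2. Five looks, one endpoint.** Under the null the test statistics at looks i and j have correlation √(Ni/Nj); for example, √(20/60) = 0.58 between the first and last. Overall error is 1 − P(|Zi| < 1.96 at all five looks). Cumulative results:

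| Look (N) | 20 | 30 | 40 | 50 | 60 |
|---|---|---|---|---|---|
| Normal theory | 5.0% | 7.7% | 9.7% | 11.4% | 12.7% |
| t-test, 1,000,000 simulated trials | 5.0% | 7.8% | 9.8% | 11.5% | 13.0% |

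**3. Sensitivity to the test and to the measures.** Overall error after five looks:

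| Decision rule (assumed) | Overall error |
|---|---|
| Rank test, continuous or three-grade score | 12.3% to 12.6% |
| Fisher's exact test, event rate 20% to 50% | 5.0% to 6.1% |
| Fisher's exact test, event rate 15% / 10% / 5% | 4.1% / 2.2% / 0.3% |
| Any of two measures, independent / correlation 0.5 | 24% / 23% |
| Any of three measures, independent / correlation 0.5 | 34% / 30% |
| Both of two measures at one look, independent / correlation 0.5 | 0.8% / 2.9% |
| All three measures at one look, correlation 0.5 | 1.0% |

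**4. Boundaries that restore 5%.** A constant boundary needs z = 2.37 at each look, or nominal p of about 0.0176 (0.0174 with t-tests). Rounded down to p<0.017, overall error is 4.9%. An O'Brien-Fleming-type boundary is c·√(60/N), with c about 2.06. The nominal levels are about 0.0004, 0.0036, 0.0117, 0.0242 and 0.0396, and t-tests at those levels give 5.0% to 5.1%.

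**5. What the stopping number shows.** Assume a true effect of 0.5 SD. Under the uncorrected rule 57.4% of trials reach significance: 18.6, 12.1, 10.2, 8.9 and 7.7% of all trials at the five looks. Dividing by 57.4 gives 32, 21, 18, 15 and 13% of the significant trials, so one truth produces every N in the range.

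The mean observed effect at that truth is 0.90 SD in significant trials, 0.63 SD in all trials and 0.28 SD in those never significant. A single test at 60 gives 0.73 SD in its significant trials, so part of the exaggeration is ordinary selection on significance and the rest comes from the repeated looks.

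**The case against.** The strongest case has four parts.

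- **It is a pilot.** The Research Plan calls it a test of feasibility, and a false positive leads to another trial rather than to a change in practice. This softens the consequence. It does not remove the problem, because significance is itself the recruitment rule and aim 2 includes efficacy in generating an immune response.
- **No test is named, so 13% is an assumption, and the error may not be inflated at all.** This is correct as far as it goes. The text does not say that any one measure suffices; if all must be significant together, error is about 3% or less. Fisher's exact test on a rare binary endpoint also stays below 5%. These cases widen the range, but the plan commits to none of them, so nothing in it secures 5%.
- **Metastasis is not affected.** This stands. Metastasis is assessed over five years and is not among the data listed before unmasking. The inflated figure applies to the immune-response comparison only.
- **Nobody says the stopping number will size the next trial.** The documents are silent on that. Aim 1 and the outcome wording make the reading plausible, and the point is conditional on it. The 0.5 SD figures are illustrative.

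**Conclusion.** The concern holds. Followed as written, the rule does not in general deliver the stated two-sided 5%. For one endpoint with a t-type test over all five looks it gives 12.7% to 13.0%, and a rank test gives nearly the same. The true figure is undefined until one endpoint and one test are named; under the assumptions examined it runs from below 5% to 34%. The stopping number is not a valid estimate of the sample size needed. This should be settled before the first unmasked look, since a boundary chosen after seeing results would not protect the error rate.

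**What to change.** Amend the sample size and unmasking paragraphs of the Research Plan, and make the analysis section agree.

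1. **Name one endpoint, with its scale, and one test for the stopping decision.** This step is essential. With p<0.017 at each look but any of two or three independent measures able to stop the trial, overall error is still about 10% or 14%.
2. **Hold overall two-sided alpha at 5%.** Either use a five-look boundary, such as p<0.017 at each look or the O'Brien-Fleming-type levels 0.0004, 0.0036, 0.0117, 0.0242 and 0.0396, or test once at a fixed number. These boundaries are examples.
3. **For aim 1, size the next trial from a bias-adjusted effect and the pooled SD with its confidence interval,** not from the N at which p crossed the line. A boundary does not cure the bias: at a true 0.5 SD, significant trials average 1.00 SD with p<0.017, against 0.90 uncorrected.

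The change needs text and one decision on endpoint and test; the maximum of 60 stays. The price is power by 60 patients:

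| True effect (assumed) | Uncorrected | p<0.017 | O'Brien-Fleming-type | Single test at 60 |
|---|---|---|---|---|
| 0.8 SD | 90% | 79% | 85% | 86% |
| 0.5 SD | 57% | 39% | 46% | 48% |

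The O'Brien-Fleming-type boundary seldom stops at 20 patients (2% at 0.8 SD, against 40% uncorrected), so average enrolment at 0.8 SD rises from 34 to 46.

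### Stopping at the first significant look and reporting only unadjusted summaries biases the observed effect upward, mainly when the true effect is small or moderate

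*Combined protocol and SAP*

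**What the plan says.** The Research Plan starts with a "minimum of 20 (10 treatment, 10 placebo) participants (up to a maximum of 60") and gives one reason for the first figure: "It is estimated that statistical significance will be reached with 20 patients". No effect size, SD or power stands behind that statement. If significance is not reached, "an additional 10 (5 treatment, 5 control) patients will be enrolled", and after that "an additional 10 patients will be enrolled and so on up to a maximum of 60 patients". Later in the same section the groups are unmasked once the laboratory and pathology data have been analysed, and "If the data reaches statistically significance, the study will not accept any more patients". A trial that is still not significant at the maximum goes no further as it stands: "If after 60 patients, significance is not achieved then further recruitment under the current protocol would not be logical", and the methodology is to be revised or the study discontinued.

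The section How will the data be analyzed says "Data will be summarized by treatment group" and lists means, medians, SDs, standard errors and 95% confidence intervals. It adds: "All hypothesis testing will be carried out at the 5% (2-sided) significance level unless otherwise specified". It names no between-arm estimate and no estimate or interval that allows for stopping on the result.

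The first Major Aim (under Hypothesis) is to find how many patients are needed to show a significant difference. The Research Plan describes the study as a pilot for a larger trial.

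**The concern.** A trial that stops because it has reached significance must have observed a difference above the threshold for its size, and that threshold is highest at the smallest size. The results that end recruitment early are therefore those in which chance has added to the effect. Ordinary means and differences from such a trial are too large on average, and nothing in the plan says so or adjusts for it.

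This is a separate matter from the type I error of repeated testing. A stricter level at each look restores the error rate but makes the exaggeration after a significant stop slightly larger.

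What is at stake is the use of the pilot's result. A reader will take the observed difference at face value. Anyone who plans the larger trial from it is likely to make that trial too small.

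**Working it through.** **Inputs from the documents.** Looks at 20, 30, 40, 50 and 60 patients, that is n = 10, 15, 20, 25 and 30 per arm; two-sided 5% at each look; stop at the first significant result.

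**Assumptions (not in the documents).** One continuous, normally distributed endpoint; two-sample t-test on cumulative data; equal arms; no dropout; true effects from 0.3 to 1.3 SD.

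**Step 1: the plan's own figure.** The 20 patients cannot be reproduced, because no effect size, SD or power is given. Working backwards at 80% power and two-sided 5%: (1.96 + 0.84) × √(2/10) = 1.25 SD, or 1.32 SD with the t distribution. At a true 0.5 SD, power at 20 patients is about 19%.

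**Step 2: smallest observed difference that can stop the trial.** In units of the observed SD it is t(0.975, 2n−2) × √(2/n):

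| Patients | 20 | 30 | 40 | 50 | 60 |
|---|---|---|---|---|---|
| Threshold (SD) | 0.94 | 0.75 | 0.64 | 0.57 | 0.52 |

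Every threshold lies above 0.5 SD.

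**Step 3: the rule simulated at a true 0.5 SD** (several hundred thousand trials). About 57% of trials reach significance. Their mean estimate is 0.84 to 0.85 SD (0.85 for stops in favour of IL-2). By stopping size the means are about 1.11 SD at 20 patients, 0.86 at 30, 0.73 at 40, 0.65 at 50 and 0.59 at 60. The other 43% end at 60 with a mean of 0.28 SD. Over all trials: 0.57 × 0.84 + 0.43 × 0.28 = 0.60 SD.

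**Step 4: comparator.** One test at a fixed 60 patients has about 48% power at 0.5 SD. Its mean estimate is 0.50 SD over all trials and 0.71 SD among the significant ones. Of the excess of 0.85 − 0.50 = 0.35 SD, 0.21 SD would therefore arise from selecting on significance at 60 patients, and 0.14 SD comes from the early looks.

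**Step 5: other true effects.**

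| True effect (SD) | Mean over all trials | Mean after a stop favouring IL-2 |
|---|---|---|
| 0.3 | 0.37 | 0.81 |
| 0.5 | 0.60 | 0.85 |
| 0.8 | 0.92 | 0.98 |
| 1.0 | 1.10 | 1.11 |
| 1.3 | 1.35 | 1.36 |

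With a per-look level of 0.0158 and a true 0.5 SD, the mean after such a stop rises from 0.85 to 0.93 SD. The unadjusted 95% interval for the difference covers about 87% of the time with no effect and 94–95% at 0.3 to 0.8 SD, so the point estimate is the main fault.

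**Step 6: consequence for sizing, if the observed effect is used.** Per arm at 80% power, n = 2 × (1.96 + 0.84)² / d² = 15.7 / d². This gives 22 for 0.85 SD, 44 for 0.60 SD and 63 for 0.5 SD; the t-test adds one to each. If the truth is 0.5 SD, 23 per arm has 38% power and the size based on 0.60 SD has about 65%, while 64 per arm is needed for 80%.

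**Step 7: what a standard correction achieves.** With known SD and a true 0.5 SD, the stagewise-ordering median-unbiased estimate lowers the mean after a positive stop only from 0.86 to 0.79 SD. It leaves stops at 20 patients, about a third of positive stops, unchanged at 1.13 SD. The matching lower 95% limit averages about 0.03 SD after a positive stop.

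**The case against.** The strongest reply is that the problem is smaller than it first appears.

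- *A reader might infer that a true 0.5 SD would simply be reported as 0.85 SD.* That holds only for the trials that stop significant; over all trials the mean is about 0.60 SD. The conditional figure still matters, because a trial that is not significant at 60 is to be revised or discontinued, so the significant trials are those likely to be carried forward.
- *A reader might blame the repeated looks for the whole excess.* Step 4 shows that more than half of it would be there with a single test at 60.
- *The effect size is chosen, not given.* This stands. The only planning statement implies about 1.3 SD at 80% power, where the exaggeration is about 4%. But the documents offer no basis for so large an effect, and the provision for up to 60 patients allows for smaller ones.
- *A reader might infer that the plan commits to sizing the larger trial on the observed effect.* It does not. The first aim seeks a number of patients without naming a method, and the Research Plan speaks of feasibility. The use is a reasonable inference and no more.
- *The model is simpler than the trial.* This stands too. No single endpoint triggers stopping: lymphocyte infiltration and circulating immunomodulators are both named, and RNA, proteomic and metabolomic data are analysed before unmasking. Testing several measures would change the figures, and no adjusted estimate can be computed until the endpoint and test are fixed.

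**Conclusion.** The concern holds in a limited form. Followed as written, the plan yields an effect estimate biased away from zero and describes no correction. The absence of a correction is read from the silence of the analysis section. At a true 0.5 SD the bias is about 0.10 SD over all trials and 0.35 SD after a significant stop. It is larger in relative terms at 0.3 SD and small from about 1 SD upward. These sizes rest on one normal endpoint, a t-test, equal arms, cumulative analysis and no dropout.

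The documents do not support saying that the larger trial will be underpowered. They support saying that it would be if the raw estimate were its planning value and the true effect were moderate. Nor would it be right to infer that a median-unbiased estimate, or its lower limit, cures the problem. The first corrects only part of the bias after a significant stop and none of it at 20 patients. The second lies too near zero to size a trial.

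**What to change.** Add to How will the data be analyzed, once the endpoint and test that trigger stopping have been named:

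> The treatment effect is the between-arm difference on the endpoint that determines stopping. It is reported unadjusted and, beside it, as the stagewise-ordering median-unbiased estimate with a confidence interval, both allowing for the looks at 20, 30, 40, 50 and 60 patients. An estimate conditional on the stage at which recruitment stopped is also given. If recruitment stopped on a significant result, the report states that the unadjusted estimate is exaggerated. The larger trial is not sized on the unadjusted estimate alone; its sample size is shown over a range of smaller effects.

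Another sequential estimate would serve, provided that it is named in advance. The stage-conditional estimate is needed because the median-unbiased one does not change a result that stopped at 20 patients. The adjusted lower limit should not be offered as a planning value.

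The cost is some programming and a reported effect that is less favourable and less precise. No patient procedure changes.

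### The decision at 60 patients rests only on missing significance, which is weak evidence against a moderate effect and does not size the larger trial

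*Combined protocol and SAP*

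**What the plan says.** The Research Plan starts from 10 patients per arm: "It is estimated that statistical significance will be reached with 20 patients". If that fails, groups of ten are added: "an additional 10 patients will be enrolled and so on up to a maximum of 60 patients". The later text on unmasking in the same section repeats the rule: "If the data reaches statistically significance, the study will not accept any more patients, if not, a further 10 patients will be incorporated". At the cap the text reads "If after 60 patients, significance is not achieved then further recruitment under the current protocol would not be logical", and the sentence goes on to name two consequences, revising the methodology or discontinuing the study.

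The Research Plan also states the pilot's purpose: "the principle of the design is to test the feasibility of proceeding to a larger and more expensive trial". The first Major Aim, under Hypothesis, begins "To conduct a pilot study to assess the number of patients needed to analyze" and defines that number as the one that gives a statistically significant difference between the arms in measures that include TILs and circulating immunomodulators.

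On testing, the section on how the data will be analyzed says "All hypothesis testing will be carried out at the 5% (2-sided) significance level unless otherwise specified". It plans means, SDs, standard errors and 95% confidence intervals in tables summarized by treatment group. It plans no confidence interval for the difference between groups and names no difference worth detecting.

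**The concern.** A p-value above 0.05 at 60 patients can arise because IL-2 does nothing to the immune measures, or because it has a moderate effect that 30 per arm is too few to show. The rule treats the two alike. A pilot meant to inform a larger trial needs the size of the difference, its precision and the SD, and the p-value supplies none of these. A promising but imprecise result would trigger revision or discontinuation, and the plan never says that a larger sample is one of the acceptable responses.

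**Working it through.** **Inputs from the documents.** Two-sided 5% tests; 1:1 allocation in the stated steps (10:10, then 5:5); looks at 20, 30, 40, 50 and 60 patients; no adjustment for repeated looks. The cap is therefore 30 per arm if the later steps stay 1:1.

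**Inputs that are assumptions.** The documents give no effect size, SD, power or single named endpoint. I take one continuous endpoint, a two-sample t-test, true standardized differences d from 0.4 to 0.8 SD, and no losses.

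**1. The plan's own figure.** The expectation of significance at 20 patients cannot be reproduced, because nothing behind it is stated. Solved backwards, 10 per arm has 80% power only at d = 1.32. The same calculation for 30 per arm gives d = 0.74.

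**2. Power and miss rate at 60.** For the single test, the noncentrality is d × √(30/2) with 58 degrees of freedom. For the plan's rule, I simulated t-tests at 10, 15, 20, 25 and 30 per arm, each at two-sided 0.05, stopping at the first significant result.

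| True difference (SD) | Power, one test at 60 | Never significant over five looks |
|---|---|---|
| 0.4 | 33% | 57% |
| 0.5 | 48% | 43% |
| 0.6 | 63% | 29% |
| 0.8 | 86% | 10% |
| 1.0 | 97% | 2% |
| 1.32 | over 99% | about 0.1% |

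The five-look column flatters the plan, because the unadjusted looks raise the type I error to about 13% for one endpoint. With each look tested at about 0.017, which holds the overall error near 5%, power at 0.5 SD is about 39%, a miss rate of about 61%.

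**3. Precision at 60.** The half-width of the 95% CI for the difference is t(0.975, 58) × √(2/30) = 2.00 × 0.258 = 0.52 SD. A result just short of significance has an estimate just under 0.52 SD and an upper limit near 0.52 + 0.52 = 1.03 SD. This is the ordinary interval; stopping on significance means its coverage is not exactly 95%.

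**4. What a larger trial would need.** For d = 0.5, 80% power in one two-sided 5% t-test needs about 64 per arm, 128 in total, or roughly twice the cap.

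**5. What a CI criterion could deliver at 60.** To exclude a difference of 0.5 SD, the upper limit must fall below 0.5, so the estimate must lie below about 0.50 − 0.52 = −0.02 SD. If IL-2 has no effect, that happens about 48% of the time.

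**The case against.** Three stronger readings are tempting, and the documents do not support them.

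- **That the rule abandons intralesional IL-2.** The sentence limits only recruitment under the current protocol and names revision before discontinuation. Nothing forbids a revised protocol with more patients.
- **That the rule contradicts the first aim.** The aim is itself worded as the number needed to reach significance, and enrolling until significance up to a cap carries that out. The gap is with the feasibility purpose, which the p-value does not serve well.
- **That 60 patients would often miss a real effect, without qualification.** This depends on the effect. If the sponsor really expects something near 1.32 SD, the rule misses almost nothing, and at 0.8 SD it misses about one time in ten.

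Two further objections carry weight. The rule names no single endpoint. If any of several measures could count as significant, never reaching significance would be less likely than the table shows, partly through false positives. And a rule to stop only when the CI excludes a margin has its own cost: with a 0.5 SD margin, a treatment with no effect would fail to meet the stopping condition at 60 about half the time.

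What survives is narrower. Both named consequences follow from non-significance alone. No stated effect size justifies 60 as the point at which non-significance is informative. The by-group summaries already planned do not include an interval for the difference.

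**Conclusion.** The concern holds in a limited form. As the only criterion at 60, non-significance is weak evidence against differences of roughly 0.4 to 0.6 SD: the chance of never reaching significance is about 57% to 29% under the plan's looks. It is good evidence against differences of about 1 SD or more. The figures assume one continuous endpoint, a t-test and 60 evaluable patients. Patients who do not complete both treatment cycles are removed, so the evaluable number may be lower; with an assumed 24 per arm, single-test power at 0.5 SD falls from 48% to 40%. The rule would be defensible if the sponsor stated that only large effects matter, but the documents do not say so. This should be changed before the first unmasking; it does not show that the trial would discard an effective treatment.

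**What to change.** - At the end of recruitment, report the between-group TIL difference with its 95% CI and the pooled SD. Adjust the interval for the repeated significance-based looks, or state plainly that it is unadjusted.
- State one worthwhile difference in TILs, on a defined scale, before the first unmasking.
- Replace non-significance as the sole criterion at 60 with a judgement of the estimate and CI against that difference. CI exclusion should inform the decision and not be the only condition for stopping, given the 48% figure above.
- Size any larger trial from the pooled SD and the worthwhile difference, and list a larger sample explicitly among the possible revisions.

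The cost is protocol wording and the work of agreeing one value in advance; this pilot needs no extra patients. The downside is that the interval at 60 may be inconclusive, in which case the decision will need judgement, and a larger trial of a treatment with no effect remains possible.
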